## **Appendix 24      Beck Depression Inventory II (BDI-II)**

To be supplied by Indivior Inc.

<http://www.pearsonclinical.com/psychology/products/100000159/beck-depression-inventoryii-bdi-ii.html?Pid=015-8018-370&Mode=summary#tab-details>

## **Appendix 25      Brief Pain Inventory (BPI) Short Form**

To be supplied by Indivior Inc.

[http://www.mdanderson.org/education-and-research/departments-programs-and-labs/departments-and-divisions/symptom-research/symptom-assessment-tools/BPI\\_UserGuide.pdf](http://www.mdanderson.org/education-and-research/departments-programs-and-labs/departments-and-divisions/symptom-research/symptom-assessment-tools/BPI_UserGuide.pdf)

1.0 Introduction

This statistical analysis plan (SAP) describes the statistical methods to be used during the final reporting and analyses of data collected for the full study (Protocol RB-US-13-0003).

This SAP should be read in conjunction with the study protocol and case report form (CRF). This version of the plan has been developed using the protocol dated 04AUG2016 and CRF dated 22SEP2016.

The SAP for study RB-US-13-0003 was developed in three stages. SAP Version 1.0 was finalized so that programming could begin earlier in the process. SAP Version 2.0 was finalized before the interim database lock and was used for the interim analysis. This SAP version 3.0 will be finalized and used for the final reporting and analysis of the full study data.

1.1 Changes from Protocol

The following changes to the analysis planned in the protocol were made:

- The addition of an analysis set (Run-In Safety Analysis Set) was made to aid in the analysis of the Run-In period.
- Electrocardiograms (ECGs) overall impression summaries will only be summarized by normal or abnormal; protocol says they should be summarized by normal, abnormal not clinically significant, or abnormal clinically significant, but there is no distinction of clinical significance for abnormal results.
- There will be no mixed-effect model for repeated measure analysis on the clinical outcome data, Clinical Opiate Withdrawal Scale (COWS), Subjective Opiate Withdrawal Scale (SOWS), and Opioid Craving Visual Analog Scale (VAS), due to the nature of the study design.
- The Clinical Outcome Assessment Analysis Set has been removed since this is a safety study.
- Total score for electronic Columbia Suicide Severity Rating Scale will not be summarized.
- Physical examination data is collected as a part of the corresponding safety assessment (i.e. adverse events (AEs), vital signs).

2.0 Study Objectives

Indivior Inc., formerly Reckitt Benckiser Pharmaceuticals Inc. (RBP) is developing RBP-6000, a long-acting formulation of buprenorphine for monthly subcutaneous (SC) injection, for the treatment of opioid use disorder (OUD).

2.1 Primary Objective

To assess the long-term safety and tolerability of RBP-6000 SC injections in subjects with opioid use disorder.

2.2 Secondary Objectives

To collect clinical outcome data with RBP-6000 SC injections in subjects with opioid use disorder.

2.3 Tertiary Objectives

To evaluate the:

- Pharmacokinetics (PK) of RBP-6000,
- Relationship between RBP-6000 PK and clinical outcome data, and
- Impact of RBP-6000 on health and economic outcomes.

Sponsor: Indivior Inc.
Protocol no: RB-US-13-0003

A stand-alone SAP will be developed for the health and economic outcomes. PK will be reported separately from the clinical study report.

3.0 Study Design

This is a multicenter, open-label, long-term Phase III safety study in which approximately 600 subjects diagnosed with opioid use disorder will be enrolled (approximately 300 subjects who did not participate in the RB-US-13-0001 study [hereafter referred to as “*de novo*” subjects] and approximately 300 subjects that completed the RB-US-13-0001 study [hereafter referred to as “roll-over subjects”]). Subject participation will be based on the Investigator’s determination that initiation or continuation of study treatment is appropriate; and, that among subjects who are continuing from the RB-US-13-0001 study, there have been no significant protocol deviations or clinically important AEs that would preclude inclusion of the subject in RB-US-13-0003.

Before receiving the first injection of RBP-6000 in this safety study, all subjects will undergo a Run-In period with SUBOXONE® (buprenorphine/naloxone) sublingual film to avoid precipitating a withdrawal syndrome and to preserve blind in subjects treated with placebo in the RB-US-13-0001 study. Subjects will be inducted onto SUBOXONE sublingual film consistent with the SUBOXONE sublingual film label; they will then complete a 1 to 11 day SUBOXONE sublingual film Dose Adjustment period.

Once subjects meet the criteria (on Day -11 to Day -1) of no significant opioid craving (≤ 20 mm on the Opioid Craving VAS and no significant withdrawal (≤ 12 on the COWS) they may receive the first SC injection of RBP-6000 (containing 300 mg of buprenorphine). Subjects with significant withdrawal signs/symptoms (defined as > 12 on the COWS) or significant cravings for opioids (defined as > 20 mm on the Opioid Craving VAS) after the end of the 2-week SUBOXONE sublingual film Run-In period will not be eligible to continue in the study and will be referred for treatment.

On Day 1 of the study (initiation of study drug injections), all subjects will receive a SC injection of 300 mg of buprenorphine in RBP-6000. Subsequent doses of RBP-6000 may be adjusted down to 100 mg and back up to 300 mg based on the medical judgment of the Investigator. After injection of RBP-6000, subjects will not be permitted to receive supplemental SUBOXONE sublingual film during the RBP-6000 treatment period. Subjects who require supplemental SUBOXONE sublingual film or other sublingual buprenorphine pharmacotherapy during the RBP-6000 treatment period will be withdrawn from the study and referred for appropriate treatment.

Subjects will return to the clinic for monthly injection visits (every 28 $-2/+4$ days) for a total of up to 12 injections for *de novo* subjects or for a total of 6 injections for roll-over subjects. ECG recordings and vital signs will be collected pre and post each SC injection. All ECGs will be interpreted by a central monitoring facility. Subject-reported injection site pain VAS scores will be collected at various times up to 1 hour after each injection. Local injection site grading will be collected at various time points starting immediately after injection and will be evaluated for pain, tenderness, warmth, itching, erythema, inflammation or swelling, and bruising using a 4-point severity scale. At each visit after injections begin, the injection site will be assessed by site staff and will also be evaluated for evidence of attempts to remove the depot.

Subjects will need to return to the clinic weekly for the first 5 weeks and biweekly (i.e., every 2 weeks) until injection 6, and monthly for the rest of the study period for urine drug screens (UDS), Timeline Followback (TLFB) interviews, opioid craving VAS evaluation, COWS and subject reported outcomes (SOWS). Subjects will continue to receive counseling (manual-guided behavioral therapy) during the study. Safety assessments will be collected at each injection visit and/or at injection follow-up visits and will include the following: vital signs, electronic Columbia Suicide Severity Rating Scale (eC-SSRS) responses, ECGs, laboratory tests (hematology, chemistry, urinalysis, and pregnancy test), concomitant medications, and AEs.

Sponsor: Indivior Inc.
Protocol no: RB-US-13-0003

Approximately 2 months prior to the scheduled end of study (EOS) visit, the subject's ongoing treatment options will be reviewed with the investigator. At the EOS, 2 transition treatment options may be offered if the subject is eligible:

- Subjects who complete RBP-6000 treatment period may be offered entry into an open label extension study of RBP-6000 (Study INDV-6000-301). Eligibility will be based on meeting the inclusion and exclusion criteria and the medical judgment of the Investigator.
- Subjects who do not meet the eligibility criteria of the extension study, or subjects who do not wish to enroll may alternatively enter a 4-week SUBOXONE transition period if deemed suitable by the investigator. Subjects should be dosed using the Investigators medical judgment. Any additional unscheduled visits required by the subject for the SUBOXONE transition will not be compensated by the Sponsor.

Subjects that did not enroll onto the INDV-6000-301 should be contacted by telephone approximately 4 weeks after EOS for a safety follow-up assessment of AEs and use of concomitant medications. The safety assessments used include evaluations of AEs, serious AEs (SAEs), discontinuations from study due to AEs; local injection site tolerability (e.g., injection site grading); injection site pain using a subject-reported VAS; suicidality using the eC-SSRS, concomitant medications; changes in clinical laboratory results; vital sign measurements; 12-lead ECGs, and physical examination results. The instruments used to measure clinical outcomes (e.g., COWS, SOWS, Opioid Craving VAS, and eC-SSRS) were developed to measure the specific symptoms exhibited by and the challenges facing opioid-dependent individuals.

3.1 Sample Size Considerations

This study is designed to assess the long-term safety, tolerability, and clinical outcomes of RBP-6000 SC injections in subjects with opioid use disorder. Approximately 300 *de novo* subjects as well as approximately 300 roll-over subjects who completed the RB-US-13-0001 study will be enrolled into this long-term safety study. The planned number of subjects was designed to ensure at least 100 subjects reach 1 year of treatment with RBP-6000 (as advised in the ICH-E1A Guideline – The Extent of Population Exposure to Assess Clinical Safety: For Drugs Intended for Long-term Treatment of Non-Life-Threatening Conditions).

3.2 Randomization

This is an open-label study and does not involve randomization.

3.3 Study Duration

The expected maximum duration of participation for *de novo* subjects is up to approximately 55 weeks consisting of up to a 7-day screening period, up to a 14-day SUBOXONE sublingual film Run-In, up to a 48-week open-label treatment period, and a 4-week follow-up and transition period when subjects will receive the same dose of SUBOXONE that they received at Day -1 and their ongoing treatment options will be reviewed.

The expected maximum duration of participation for roll-over subjects is up to approximately 31 weeks, consisting of up to a 7-day screening period, up to a 14-day SUBOXONE sublingual film Run-In, a 24-week open-label treatment period, and a 4-week follow-up and transition period when they will receive the same dose of SUBOXONE that they received at Day -1 and their ongoing treatment options will be reviewed.

If at least 100 subjects reach 1 year of exposure to RBP-6000 in RB-US-13-0001 and RB-US-13-0003, the study may be stopped early, and all remaining subjects will complete EOS procedures and enter the SUBOXONE Transition Period/Safety Follow-up.

Subjects who receive at least 1 dose of RBP-6000 and discontinue the trial for any reason will be required to complete the Early Termination (ET) visit.

4.0 Study Variables and Covariates

4.1 Primary Variables

The following variables will be evaluated to assess the safety and tolerability of RBP-6000:

- Incidence of treatment-emergent adverse events (TEAEs).
- Changes in clinical laboratory results.
- Vital sign measurements.
- Other variables related to safety
 - 12-lead ECGs.
 - Medical history.
 - Suicidality using the eC-SSRS.
 - Prior and concomitant medications.
 - Local injection site tolerability (e.g., injection site grading).
 - Injection site pain using a subject-reported VAS.
 - Physical examination results.

4.2 Secondary Variables

The following secondary variables will be evaluated to analyze clinical outcomes:

- COWS total score.
- SOWS total score.
- Opioid Craving VAS total score.
- Self-reported illicit drug use.
- Percentage of negative urine drug screen samples.

4.3 Tertiary Variables

- PK of RBP-6000.
- Health economic and outcome data (to be analyzed in a separate SAP)
 - Beck Depression Inventory.
 - Brief Pain Inventory.
 - EuroQoL EQ-5D-5L.
 - 36-Item Short Form Health Survey.
 - Medication Satisfaction Questionnaire.
 - Healthcare Resource Utilization.
 - Treatment Effectiveness Assessment.
 - Addiction Severity Index Lite.

Sponsor: Indivior Inc.
Protocol no: RB-US-13-0003

TEAEs are those that started following the first dose of RBP-6000 in this study or were present prior to the first dose of RBP-6000 in this study regardless of causality and increased in severity following administration of RBP-6000 regardless of causality ≤30 days after the last dose of RBP-6000. All AEs which change in severity or relationship to RBP-6000 are assigned a new start date and captured as a new AE. AEs include those events that are ongoing at the time a subject rolls-over from the RB-US-13-0001 but these events will not be considered treatment-emergent.

Sponsor: Indivior Inc.
Protocol no: RB-US-13-0003

Run-In Adverse Events

An AE for the run-in period is an AE that either commenced during the run-in period or was present prior to the initiation of run-in, but increased in severity during run-in, regardless of causality, and prior to the first injection of RBP-6000.

Outcome of Death

Any AE with an outcome of fatal or study discontinuation due to death.

Subjective Opioid Withdrawal Scale Total Score

The SOWS total score is defined as the sum of the responses to the 16 questions as indicated by the subjects on how they feel at the time of completed the questionnaire including anxiousness, yawning, perspiring, teary eyed, runny nose, goosebumps, shaky, hot flushes, cold flushes, bones and muscle achiness, restlessness, nausea, vomiting, muscle twitching, stomach cramps, and feeling like using now. Each answer to a corresponding question is assigned a value between 0 and 4. If 3 or more responses are missing, then a total score will be set to missing. If less than 3 responses are missing, then the total score will be normalized.

Suicidal Ideation Scoring

The suicidal ideation score ranges from 0 to 5 and depends on the answers to the suicidal ideation portion of the eC-SSRS. The score is the maximum suicidal ideation category (in the following order: 1 = wish to be dead, 2 = Non-specific active suicidal thoughts, 3 = active suicidal ideation with any methods (not plan) without intent to act, 4 = active suicidal ideation with some intent to act, without specific plan, and 5 = active suicidal ideation with specific plan and intent) present at the assessment. If all answers to these questions are "No" then the suicidal ideation score is 0.

Suicidal Ideation Intensity Rating:

The suicidal ideation intensity rating is the sum of the five intensity item scores to create a total score (range 0 to 25). The five intensity items include frequency, duration, controllability, deterrents, and reason for ideation. Each item is scored from 0 to 5 with 5 representing the most severe intensity.

Suicidal Behavior Scoring

The suicidal ideation score ranges from 0 to 5 and depends on the answers to the suicidal behavior portion of the eC-SSRS. The score is the maximum suicidal ideation category (in the following order: 1 = preparatory acts or behavior, 2 = aborted attempt, 3 = interrupted attempt, 4 = actual attempt, and 5 if the subject has an AE with a preferred term of completed suicide. If all answers to these questions are "No" and the subject does not have an AE with a preferred term of completed suicide then the suicidal behavior score is 0.

Treatment Duration (weeks)

Treatment duration will be defined as $(\text{treatment stop date} - \text{treatment start date} + 1)/7$ where treatment stop date is defined as date of last RBP-6000 injection + 28 days.

Sponsor: Indivior Inc.
 Protocol no: RB-US-13-0003

Percentage of Urine Drug Screen and Self-Report Results

Subjects' self-reported illicit drug use from the TLFB and results from the UDS will be combined into a single endpoint in the following manner:

- If both the TLFB and the UDS have a negative result at a particular visit, then the visit will be considered to have a negative result at that visit.
- If either the TLFB or UDS, or both, have a non-negative result at a particular visit, then the visit will be considered to have a non-negative result at that visit.
- To be conservative, missing UDS or TLFB data will be imputed as non-negative.

Urine Drug Screen Result for Opioids	Self-Report of Illicit Opioid Use Result	Overall Result
Nonnegative	Nonnegative	Nonnegative
Nonnegative	Negative	Nonnegative
Negative	Nonnegative	Nonnegative
Negative	Negative	Negative

Treatment Success

A subject is defined as a treatment success if $\geq 80\%$ urine samples negative combined with self-reports negative.

Visit Window for Remapping of Early Termination visit

Duration will be derived in days as (ET visit date – treatment start date) + 1.

Sponsor: Indivior Inc.
 Protocol no: RB-US-13-0003

Visit window for safety and efficacy assessments.

Study Visit	Lower Window for Analysis Day (ADY)	Upper Window for ADY
Week 1 Day 1	1	1
Week 1 Day 2	2	5
Week 2 Day 8	6	12
Week 3 Day 15	13	19
Week 4 Day 22	20	26
Week 5 Day 29	27	38
Week 7 Day 43	39	54
Week 9 Day 57	55	68
Week 11 Day 71	69	82
Week 13 Day 85	83	94
Week 15 Day 99	95	110
Week 17 Day 113	111	122
Week 19 Day 127	123	138
Week 21 Day 141	139	166
Week 25 Day 169	167	194
Week 29 Day 197	195	222
Week 33 Day 225	223	250
Week 37 Day 253	251	278
Week 41 Day 281	279	306
Week 45 Day 309	307	335

If an ET visit/assessment happens any time between Day 1 and prior to End of Study visit, the following approach (Table) should be adopted to remap those ET visit to applicable study visit week based on the ADY variable value, defined as date of assessment – date of first dose + 1, of the ET date variable.

If Lower Window <= ADY (of ET date) <= Upper window, then set appropriate AVISIT value based on the above CRF study visits.

After re-mapping the ET visits to any of study visit weeks, if there are multiple records falling within the same week window, latest one with non-missing result will be flagged in analysis datasets and considered for analysis of by visit summary tables and figures.

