#### 6.10.10 Treatment-Emergent Adverse Events

A TEAE is an AE that either commenced following initiation of study drug or was present prior to the initiation of study drug, but increased in frequency or severity following initiation of treatment, regardless of causality.

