## 9 PLANNED STATISTICAL METHODS

### 9.1 General Considerations

A Statistical Analysis Plan (SAP) will be prepared after the protocol is approved and before database lock occurs. The SAP will provide further details regarding the definition of analysis endpoints, data handling rules, and the statistical methodology to be used to address all study objectives. The SAP will also include formats for the summary and analysis tables, listings, and graphical displays.

This section describes methods for sample size determination, analysis populations, and planned analyses for, safety, PK, and clinical outcomes endpoints. Additional unplanned analyses may be required after all planned analyses have been completed. Any unplanned analyses will be clearly identified in the clinical study report. Any deviations from the analyses described below will be included in the SAP, which will form Appendix 16.1.9 of the clinical study report.

Continuous variables will be summarized using descriptive statistics such as means, standard deviations (SD), medians, minimums, and maximums. Categorical variables will be reported as frequency counts (including number missing) and the percentage of subjects in corresponding categories. Individual subject data will be presented by subject in data listings. Data listings will include all data collected from the initial screening visit to the end of study for all subjects enrolled.

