#### 9.5.1.1 Adverse Events

All AEs will be coded using the most up-to-date version of the Medical Dictionary for Regulatory Activities (MedDRA) and reported to the FDA. AEs that began more than 30 days after the last study subject assessment day will not be included in the safety analysis. Only TEAEs occurring post administration of RBP-6000 will be included in the safety analysis (See [Section 6.10.10](#)).

The incidence of AEs (number and percent of subjects reporting the AE at least once during the study) will be summarized for all AEs, by the relationship to study drug and by severity.

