7. A PK sample will be taken as soon as possible after any SAE is reported. If possible, an additional sample should be collected when the SAE has been resolved.
8. Assessments should be performed prior to RBP-6000 injection and at approximately the same time each day  $\pm 2$  hours.
9. Local injection site grading will be performed at time of SC injection (within 10 minutes) and 1 hour ( $\pm 15$  minutes.)
10. Injection Site Pain VAS will be completed by the subject within 1 minute after completion of the injection and then at 5, 10, 15, 30, and 60 ( $\pm 5$  minutes) post-completion of injection.
11. Injection site will be evaluated for evidence of attempted removal.
12. Additional unscheduled visits for behavioral therapy may be added at the Investigator's discretion.
13. For roll-over subjects, the procedures at Week 25/Day 169 will serve as the EOS assessments. For *de novo* subjects who discontinued participation in the study after receiving RBP-6000, the procedures at Week 25/Day 169 will serve as the ET assessments.
14. IXRS contacted to confirm study completion or discontinuation status (date and reason for discontinuation).
15. Complete examination (excluding pelvic, breast, and rectal), including general appearance, skin, head, eyes, ears, nose, throat, neck, thyroid, chest/lungs, heart, abdomen, lymph nodes, extremities, and a brief neurological assessment.
16. Subject's alternative treatment options should be assessed up to two months before EOS. At the EOS visit, if eligible, subjects may enroll in study INDV-6000-301. Alternatively, subjects can start an optional 4 week SUBOXONE program (based on Investigator's discretion).
17. Collect information for the Employment/Support Status, Alcohol, Drug, Legal, Family/Social, and Psychological section only. Follow-up version of the questionnaire (only circled items, no lifetime recall).
18. Complete all ASI-Lite scales. Follow-up version of the questionnaire (only circled items, no lifetime recall).
19. Subjects should be contacted by telephone at 24 hrs ( $\pm 4$  hours) and will be assessed for AEs and any changes to Con Meds. Subjects are not required to return to the site unless the investigator deems it medically necessary.
20. Subjects should be contacted by telephone in order to assess for AEs or Con Meds. Subjects are not required to return to the site unless the investigator deems it medically necessary. Subjects enrolled onto INDV-6000-301 are not required to be contacted.

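### SAP 5.0 changes the protocol's TEAE rule without listing it in SAP 1.1; on one reading, and if AEs are captured up to the safety call, 26 nominal days of AE onset in completers leave the TEAE tables

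*SAP*

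**What the plan says.** - **SAP 5.0, TEAE definition.** One sentence holds two clauses: AEs that began after the first RBP-6000 dose, and AEs present before it that "increased in severity following administration of RBP-6000 regardless of causality ≤30 days after the last dose of RBP-6000". No punctuation shows which clause the time limit governs. The next sentence adds: "All AEs which change in severity or relationship to RBP-6000 are assigned a new start date and captured as a new AE".
- **Protocol 6.10.10.** There are again two clauses, but a pre-existing AE qualifies if it "increased in frequency or severity following initiation of treatment, regardless of causality". No end date is given.
- **Protocol 9.5.1.1.** This section applies the 6.10.10 definition and sets the only time limit: "AEs that began more than 30 days after the last study subject assessment day will not be included in the safety analysis".
- **Declaring changes.** Protocol 9.1 leaves endpoint definitions and data handling to the SAP and adds: "Any deviations from the analyses described below will be included in the SAP". SAP 1.1 begins "The following changes to the analysis planned in the protocol were made" and gives six items: the Run-In set, ECG categories, no mixed model, removal of the outcome set, the eC-SSRS total, and physical examination. None concerns TEAEs.
- **AE contact after EOS.** In SAP 3.0, subjects not entering INDV-6000-301 "should be contacted by telephone approximately 4 weeks after EOS for a safety follow-up assessment of AEs". Protocol 3.1 agrees, and the schedules in Appendices 3 and 5 mark an AE assessment at that call (Appendix 3, footnote 20: "Subjects should be contacted by telephone in order to assess for AEs or Con Meds"). But protocol 6.10.1 ends reportable AEs at the last EOS/ET visit or the start of extension treatment, and 6.10.3 ends capture when the subject completes the study.
- **Recording severity.** Protocol 6.10.2 and 6.10.4 tell sites to keep a single event at its maximum severity.

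**The concern.** TEAE incidence heads the list of primary variables in SAP 4.1, and the study's objective is long-term safety. A time limit that can be attached in two ways lets two programmers build different TEAE flags from the same data. A reader who relies on SAP 1.1 would not learn that the rule differs from the protocol's.

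The days at issue matter clinically. For completers who do not continue RBP-6000, the call is the only planned AE contact after EOS. Events linked to stopping treatment could be reported there first, and the drug-withdrawal table in SAP 9.6.1.5 counts TEAEs only. The product is also a long-acting depot. Protocol 1.4.2 gives mean terminal half-lives of 1078 hours (50 mg) to 1573 hours (200 mg) after single doses. That is 1078/24 = 44.9 to 1573/24 = 65.5 days, so a cut-off 30 days after the last dose falls within one half-life at the doses reported.

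**Working it through.** **Inputs** (nominal days, protocol Appendices 3 and 5):

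| | Roll-over | De novo |
|---|---|---|
| Last injection | 141 | 309 |
| EOS | 169 | 337 |
| Safety call | 197 | 365 |

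**1. SAP cut-off if the limit covers new onset.** Last injection + 30: 141 + 30 = Day 171; 309 + 30 = Day 339.

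**2. Days between cut-off and call.** 197 − 171 = 26 (Days 172 to 197); 365 − 339 = 26 (Days 340 to 365). This is 26 of the 197 − 141 = 56 days from last injection to call, or 46%. The EOS visit and the call each have a −2/+4 day window. If each is counted from the preceding visit (an assumption), the gap runs from 56 − 4 − 30 = 22 to 56 + 8 − 30 = 34 days.

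**3. The same days under protocol 9.5.1.1.** If EOS is the last assessment, the limit is 169 + 30 = Day 199 or 337 + 30 = Day 367. If the call is the last assessment, it is 197 + 30 = Day 227 or 365 + 30 = Day 395. Either way, the protocol keeps every day up to the nominal call.

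**4. If AE capture stops at EOS** (protocol 6.10.1, 6.10.3). Nominal EOS, Day 169 or 337, comes before the cut-off, so 0 days are lost. With EOS at +4 and the last injection on its nominal day, 173 − 171 = 2 days are lost; other placements within the windows leave a few days at most.

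**5. If the limit covers worsening only.** No new-onset days are lost. New-onset TEAEs then have no end date, which also differs from protocol 9.5.1.1. The limit may do nothing at all: a late worsening, recorded as a new AE, starts after the first dose and so enters through the first clause.

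**6. Recording rule.** Take an AE that began during run-in and worsened after the first injection. Under SAP 5.0 the worsening is a new record with a post-injection start date. Under protocol 6.10.2 and 6.10.4 there is one record, with a pre-injection start and the maximum severity. If sites followed the protocol, there may be no worsening date to test, and the event can be missed as a TEAE.

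**The case against.** The strongest reply is that the rule is not hidden. Protocol 9.1 assigns definitions to the SAP, the SAP prints this one in 5.0, and only the entry in 1.1 is missing. That is fair, and the charge should go no further than that omission. But 1.1 is where a reader looks for changes, and it reports smaller ones.

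Second, a fixed 30-day window is uniform across subjects and close to the SAP's own end of exposure, 28 days after the last injection (5.0, 9.4). This stands as a reason to keep a 30-day view. It does not resolve which clause the limit governs.

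Third, the 26 days depend on two conditions that the documents leave open. This stands in full.

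A reader might also infer four stronger things, none of which the documents support:

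- **That AEs are lost from the report.** SAP 9.6.1.1 lists all recorded AEs, including those that are not TEAEs.
- **That SAE tables will disagree with the TEAE overview.** SAP 9.6.1.2 does not say whether its tables are limited to TEAEs. The table shells, a separate document (SAP Appendix 3), would be needed to tell.
- **That roll-over events which worsen are left undefined.** The new-record rule largely answers this: the worsened record starts after the first dose, and the ongoing record is the one excluded.
- **That dropping frequency changes the counts.** Protocol 6.10.2 does not list it among the recorded AE items, and the CRF is not in the documents.

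**Conclusion.** The point holds and should be fixed. Four things are certain from the text: the limit moves from last assessment to last dose, its scope is ambiguous, frequency is dropped, and SAP 1.1 declares none of this. The conflict over recording severity is equally plain; its effect on the data depends on what sites did.

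The loss is conditional. It needs the limit to cover new onset and AE capture to run to the call. Then, for completers not entering INDV-6000-301, 26 nominal days of AE onset leave the TEAE tables (SAP 9.6.1.1) and the special-interest tables (9.6.1.5 to 9.6.1.11), although protocol 9.5.1.1 would keep them. If either condition fails, the loss is nil or a few days. Early terminators are not modelled, because their gap depends on the ET date.

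The number of AEs affected cannot be worked out and may be small. The documents give no late AE rate, and a late event in a subject already counted for that preferred term does not change its incidence.

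**What to change.** - In SAP 5.0, state one TEAE window for both new onset and worsening, from the first RBP-6000 injection to the last AE contact (the safety call, or the start of INDV-6000-301).
- Show onsets up to 30 days and more than 30 days after the last dose in separate rows. This keeps the uniform 30-day view and makes late events and unequal follow-up visible.
- Reconcile the severity-recording rule (SAP 5.0 against protocol 6.10.2 and 6.10.4) and the end of AE capture (protocol 6.10.1 and 6.10.3 against protocol 3.1, Appendices 3 and 5, and SAP 3.0).
- Declare the window change and the dropped frequency criterion in SAP 1.1. Restore frequency only if the CRF records it.

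The cost is SAP wording, one end-date rule and one flag on AEs already collected. SAP 1.0 describes version 3.0 as still to be finalized. Worsening dates may need queries if sites kept one record per event. TEAE counts may rise slightly, some late events may reflect SUBOXONE or stopping treatment, and subjects entering the extension have shorter follow-up; the separate rows let a reader see this.
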